THE OVERALL HYPOTHESIS TO BE TESTED IN THIS TRIAL is that the early introduction of combination therapy of corticosteroids and either MTX or CsA will prove more effective and safe than corticosteroids alone in the treatment of JDM.

Trial Design and Duration. Two-year single-blind (assessor blinded to treatment arm of subject), randomised, actively controlled, multi-centre, international prospective, superiority trial of different combination of drugs. Patients will be then followed for up to 5 years for the evaluation of long term morbidity and mortality.

Dose Regimen (see figure 1):

3 daily pulses of intravenous (iv) methylprednisolone (30 mg/kg/pulse max 1 g/pulse) followed by randomisation into one of these 3 groups.

Induction of remission

Group 1 prednisone or equivalent (PDN): PDN 2 mg/kg/day (see below for rules regarding PDN administration);

Group 2 PDN+cyclosporine A (CsA): PDN 2 mg/kg/day + CsA 5 mg/kg/day in 2 oral doses.;

Group 3 PDN + methotrexate (MTX): PDN 2 mg/kg/day + MTX 15-20 mg/m² once per week. Patients treated with MTX will receive concomitant folic or folinic acid according to the attending physician decision.

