Primary Outcome Measures after 24 months of treatment: a) time to clinical remission on medication defined as normal muscle strength and physician global assessment of disease activity equal to 0; b) time to flare of the disease defined as at least 20%, worsening from the previous evaluation value in 2 of any 6 JDM core set measures with no more than 1 of the remaining improved by more than 30% (muscle strength excluded).

Effectiveness: the rate of retention on treatment will be used as main measure of effectiveness.

Secondary Outcome Measures. Change over time in the individual components of the JDM core set of variables; time to muscle enzymes normalisation; frequency of drop-out of suggested steroids use; frequency of drop-out for inefficacy of treatment.

Safety Parameters.

- 1) Incidence of adverse events (AE):
 - a) Number of patients discontinuing trial due to on-therapy conditions and AE possibly, probably, or definitely related to the experimental therapy, and listing of AE that cause discontinuation.
 - b) Number of patients for whom the dosage was lowered, or withheld temporarily, due to AE, and listing of the specific AE that caused such action.
 - c) Complete list of AE by system.
- 2) Incidence of clinically significant changes in laboratory parameters.
- 3) Drop out rate due to toxicity.

Inclusion Criteria. Each patient must meet all the following criteria in order to participate in this trial:

- 1) Newly diagnosed and untreated children (only treatment with 1 NSAID is allowed and/or prednisone >1 mg/kg/day for no more than 1 month from diagnosis) with probable or definite diagnosis of JDM according to the Bohan and Peter criteria (12;13). If a muscle biopsy will be performed (optional) it will be read by the pathologists of the participating centres (light and immunofluorescence). Slides of paraffin-embedded sections from all patients will be re-viewed by a blinded myopathologist at PRINTO.
- 2) Age at enrolment \leq 18 years.
- 3) Female of child-bearing potential must have a negative pregnancy test at the beginning of the trial, and then every 3 months. If sexually active, they must agree to use adequate contraception, throughout study participation, and must have no intention of conceiving during the course of the study. Post-pubertal males must have no plans to father a child during the study and agree to use adequate birth control methods if sexually active.

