Statistical Analysis. The values at the final visit for the core set variables will be compared to the baseline values. Furthermore, patients will be dichotomously classified as "responders" or "non-responders" according to the validated JDM definition of improvement. Descriptive statistics will be used for reporting adverse events. For proportional data the chi-square test, or where appropriate the Fisher's exact test, will be applied. For continuous variables the t-test procedure or the ANOVA, will be applied as appropriate. Non parametric ANOVA will be applied in case of ordinal data or not-normally distributed variables; the Dunnett test will be used as a posterior test. Treatment effect size will be calculated by dividing the difference between the baseline and the final visit value, by the standard deviation of the first visit value. Survival analysis with censored data will be used in order to evaluate time to remission and time to flare. Survival curves will be drawn with the Kaplan-Meyer method and compared with the log rank test. For multiple hypothesis testing, alpha level is set at 0.01. Emphasis will be placed on the intention-to-treat approach rather than on analysis of only the completers of the trial. All analysis will be done in a blinded manner.

Table: Time Oriented Table and duration time for each task

| Task No | Months | 1 | 2 | 3 | 4 | 5 | 6 | 7 | 8 | 9 | 10 | 11 | 12 | 13 | 14 | 15 | 16 | 17 | 18 | 19 | 20 |
|---------|--|---|---|---|---|---|---|---|---|---|----|----|----|----|----|----|----|----|----|----|----|
| 1 | Personnel selection and training | | | | | | | | | | | | | | | | | | | | |
| 1 | Translation of material | | | | | | | | | | | | | | | | | | | | |
| 1 | Data base and case report form development | | | | | | | | | | | | | | | | | | | | |
| 1 | Submission to ethics committee | | | | | | | | | | | | | | | | | | | | |
| 2 | Trials enrolment | | | | | | | | | | | | | | | | | | | | |
| 3 | Interim analysis | | | | | | | | | | | | | | | | | | | | |

| Task No | Months | 21 | 22 | 23 | 24 | 25 | 26 | 27 | 28 | 29 | 30 | 31 | 32 | 33 | 34 | 35 | 36 | 37 | 38 | 39 | 40 |
|---------|---------------------------|----|----|----|----|----|----|----|----|----|----|----|----|----|----|----|----|----|----|----|----|
| 2 | Trials enrolment | | | | | | | | | | | | | | | | | | | | |
| 2 | Trial long term follow-up | | | | | | | | | | | | | | | | | | | | |
| 3 | Interim analysis | | | | | | | | | | | | | | | | | | | | |

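### Adverse events are to be reported as patient counts and a list with no time-at-risk denominator, so if retention differs by arm and recording stops at drop-out, the better-retained arm can look more toxic than it is

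*Protocol*

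**What the plan says.** The Safety Parameters section of the protocol lists five measures:

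- 1a: "Number of patients discontinuing trial due to on-therapy conditions and AE possibly, probably, or definitely related to the experimental therapy", with a listing of the causes.
- 1b: "Number of patients for whom the dosage was lowered, or withheld temporarily, due to AE", again with a listing.
- 1c: "Complete list of AE by system".
- 2: "Incidence of clinically significant changes in laboratory parameters".
- 3: "Drop out rate due to toxicity".

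Item 1 is headed as an incidence, but its three parts are two patient counts and a list. The incidence in item 2 and the rate in item 3 have no stated denominator.

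The Statistical Analysis section says of AEs only that "Descriptive statistics will be used for reporting adverse events". It assigns survival methods with censoring to remission and flare, not to AEs.

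Three other statements bear on the point:

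- Under Effectiveness, "the rate of retention on treatment will be used as main measure of effectiveness".
- The overall hypothesis is that early combination therapy "will prove more effective and safe than corticosteroids alone in the treatment of JDM".
- The Dropout Criteria keep dropped children in the efficacy analysis and do not mention safety, while the long-term follow-up paragraph has all patients followed for five years.

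**The concern.** A count of patients with an AE depends on the rate at which AEs occur and on how long each child is observed. In this trial, time on treatment is itself an outcome. If an arm does better on the main effectiveness measure, its children spend more months in which an AE can occur and be recorded. An unadjusted count would then charge part of the benefit to that arm as apparent toxicity. Because the hypothesis joins effectiveness and safety, the comparison at stake is the safety half of the trial's own claim. The protocol allows for unequal follow-up in two efficacy endpoints but not here.

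**Working it through.** **What the plan supplies.** It gives no AE rate and no retention figure by arm, so there is no safety figure to reproduce. The related figures are the 24-month active period, one drop-out allowance of 15% for all arms, 40 children per arm, and 6-month response of 83% (combination) and 53% (prednisone alone).

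**What is assumed.** Month-24 retention R of 60%, 70% or 85%; a constant exit rate; a constant AE rate L = 0.03 per month, unrelated to exit; no AE recorded after exit.

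**Formulas.** Exit rate m = −ln(R)/24. Mean months on treatment = (1 − R)/m. Crude share with at least one AE = L/(L + m) × [1 − exp(−24(L + m))].

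| R | L | m | Mean months | Crude share | Of 40 |
|---|---|---|---|---|---|
| 60% | 0.03 | 0.0213 | 18.8 | 41.4% | 16.6 |
| 70% | 0.03 | 0.0149 | 20.2 | 44.1% | 17.6 |
| 85% | 0.03 | 0.0068 | 22.2 | 47.8% | 19.1 |
| 85% | 0.0255 (15% lower) | 0.0068 | 22.2 | 42.6% | 17.0 |

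**Equal true rates.** The 85% arm has 22.2/20.2 = 1.10 to 22.2/18.8 = 1.18 times the exposure. It shows 47.8 − 44.1 = 3.7 to 47.8 − 41.4 = 6.4 points more children with an AE.

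**A 15% lower true rate in the 85% arm.** Observed in full for 24 months, the shares would be 1 − exp(−0.03 × 24) = 51.3% and 1 − exp(−0.0255 × 24) = 45.8%, a gap of about 5.5 points. Against a comparator retaining 70%, the crude gap is 44.1 − 42.6 = 1.5 points, so most of the advantage is hidden. Against 60%, the order reverses (42.6% v 41.4%), by less than half a child per 40. The comparator's crude share is 42.5% at 64% retention and 42.8% at 65%, so the reversal ends between those two values.

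**The plan's own drop-out.** With 15% leaving in every arm, both arms show 47.8% at equal rates. There is no distortion.

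**Upper case from the plan's response rates.** Suppose every 6-month non-responder leaves at month 6. Months per child are 0.83 × 24 + 0.17 × 6 = 20.9 and 0.53 × 24 + 0.47 × 6 = 15.5, a ratio of 1.35 in event counts at equal rates. With a 24-month AE risk of 30%, that is 10.5 v 8.0 children of 40; with 60%, 21.3 v 16.6. With 15% v 25% leaving at month 6 and a 30% risk, it is 10.7 v 9.9.

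**Would one overall rate per patient-year cure it?** Only if the AE rate is constant. The protocol's suggested prednisone dose falls steeply over the first six months, so a constant rate is doubtful. Take 8% per month to month 6 and 1.3% after (assumed), equal in both arms, with retention of 85% v 60%:

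- Exposure in months 0–6 is 5.88 v 5.63 months per child, and in months 7–24 it is 16.27 v 13.16.
- Overall rate, 85% arm: (0.08 × 5.88 + 0.013 × 16.27)/22.15 = 0.0308 per month.
- Overall rate, 60% arm: (0.08 × 5.63 + 0.013 × 13.16)/18.79 = 0.0331 per month.
- The ratio is 0.93, so the longer-retained arm looks about 7% safer with no true difference.

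Rates within each period are equal, and so is a time-to-first-AE curve that censors at exit.

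**The case against.** The strongest reply is that the protocol contains no error here. Descriptive reporting does not exclude exposure-adjusted rates, two of the safety items speak of an incidence or a rate, and AE denominators are routine content of a statistical analysis plan, which is not shown. This stands in part: nothing is forbidden, and the point is an improvement. But the patient counts in 1a and 1b are chosen in the protocol itself, and its censored-data methods are assigned only to efficacy endpoints.

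A reader might infer that exit rates are expected to differ by arm. The protocol does not say so. Its only drop-out figure is a common 15%, and no retention difference is quantified. A difference is only what success on the main effectiveness measure would imply.

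A reader might also infer that the error always runs against the combinations. That is not supported. It needs AE recording to stop at exit, which the Dropout Criteria and the long-term follow-up paragraph leave open. It needs AEs spread over time: under the front-loaded pattern used in the working, the crude gap at 85% v 60% retention is 49.1 − 45.5 = 3.6 points instead of 6.4. Toxicity also shortens retention, so items 1a and 3 can move the opposite way, and added methotrexate or cyclosporine could lower retention.

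**Conclusion.** The point holds in conditional form, as a minor and nearly free improvement. The AE measures have no time-at-risk denominator in a trial whose main effectiveness measure is time on treatment, so crude counts can make the better-retained arm look more toxic. Under the assumptions stated, the size is nil at equal drop-out and roughly 4 to 6 percentage points of children with an AE at 85% v 70% or 60% retention. A 15% true advantage is mostly hidden at 70% comparator retention and reversed only below about 64 to 65%. Retention by arm, the AE rate and its shape over time, and the end of recording at exit are assumptions, not facts from the protocol. The documents do not support a claim that the plan will make the combinations look worse.

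**What to change.** In Safety Parameters and Statistical Analysis, keep the patient counts and add:

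1. By randomised arm to month 24, the cumulative incidence of first AE, and of key AEs, by censored-data methods with confidence intervals. Say whether exit from treatment is a censoring or a competing event, because the two answer different questions. Censoring at exit removes the dependence on retention if exit is unrelated to AE risk. With exit as a competing event and otherwise complete follow-up, the month-24 value equals the crude share; it describes what children experienced but does not remove the distortion.
2. AE rates per patient-year on study treatment, split into months 0–6 and 7–24, not one overall rate.
3. A statement of whether AEs are collected after a child is dropped, reconciling the Dropout Criteria with the five-year follow-up of all patients.

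The cost is a few extra tables. Scheduled visits, the weekly dose diary and the early-termination form should supply most of the dates. The protocol asks for the reason for termination but does not name a stop date, so the form should be checked for one.

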- 4) Ability to comply with the entire study procedures, ability to communicate meaningfully with the investigational staff, competence to give written informed consent; to be applied to the parents and/or patients, as appropriate
- 5) Duly executed, written, informed consent obtained from the parents/patient.

Exclusion Criteria. Any of the following will exclude a patient from this trial:

- 1) Neutrophil count $<1,500/\text{mm}^3$ and/or platelet count $<50,000/\text{mm}^3$
- 2) Demonstration of cutaneous or gastrointestinal ulceration of JDM related pulmonary disease or cardiomyopathy at the time of diagnosis.
- 3) History of poor compliance.
- 4) Evidence of current use of alcohol or illicit drugs abuse.
- 5) Live vaccines not allowed during the entire duration of the trial.

Dropout Criteria. Patients will be considered "treatment failures", and dropped from the trial but included in efficacy analysis, if any of the following will occur during the active period of the trial.

- 1) Non compliance with study medication administration
- 2) Enrolment in other therapeutic trials.

Feasibility study for sample size calculation: from the analysis of the 295 patients with JDM enrolled in a previous PRINTO study (EU contract QLG1-CT-2000-00514) (4) it can be inferred that the network can enrol in a 2 years frame up to 190 children with less than 12 months disease duration (of whom 140 with disease duration less than 6 months).

Sample size calculation for superiority trial. We used the PRINTO JDM definition of improvement (see previous section "definition for primary outcome") (4) for sample size calculation for superiority trials.

We carried out sample size calculations based on the information obtained from a study on JDM patients conducted by PRINTO with a previous grant (contract EU contract QLG1-CT-2000-00514). In the study a total of 284 JDM patients with a mean age at onset of 7.6 years (Standard Deviation [SD] 3.9) the observed improvement rate was 83% after 6 months of therapy with PDN combined with MTX or CSA. We estimated that the group treated only with PDN will have a response rate equal to 53%.

Using the sample size calculation for superiority trials and considering a drop out rate of 15%, a sample size of **40 patients in each group for a total of 120 patients**, will be required. The trial will have 0.8 power for comparisons of the combined treatment arms (PDN+MTX or PDN+CSA) to the reference treatment arm (PDN alone).

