If enrolment will proceed faster than expected we will collect 54 patients per arm for a total of 162 patients, 0.9 power, 0.05 type I error.

Below is a table with different sample size calculations, using different levels of power.

| Variable | PDN treatment | delta | alfa | Power | N per arm | Drop-out N/(1-0.15) |
|-----------------|---------------|-------|------|-------|-----------|---------------------|
| PRINTO JDM def. | 53 | 30% | 0.05 | 0.8 | 34 | 40 |
| PRINTO JDM def. | 53 | 30% | 0.05 | 0.9 | 46 | 54 |

Procedures in the Case of Adverse Events. In the event of clinical or laboratory AE, the attending physician should make the clinical decision as to which medication is most likely the cause of the AE. The suspected medication (experimental or allowed) should be stopped or dosage reduced for 1 or 2 weeks. If the AE disappears or significantly ameliorates then the medication will be reinstated. If the AE does not disappear the physician will either drop the patient from the trial, or repeat the procedure with one of the remaining drugs. The drug that was initially discontinued (experimental or allowed) may be reinstated (as deemed appropriate by the attending physician), once it has been shown not to be the cause of the AE.

Withdrawal From the Trial. The attending physician will determine, clinically, if a patient should be removed from the trial, stating the reason for the early termination on the appropriate

form. The attending physician will be also responsible for reporting all clinically significant drug related AE. These will be graded on a three-point scale (mild, moderate, severe), and the relationship with the study medication will be assessed as definite, probable, possible, unlikely or no association as defined in the AE form. Any unexpected, life threatening or fatal AE will be reported by telephone within 12 hours after the AE, to the coordinating centre, followed by detailed medical description of the AE, along with copies of all pertinent medical records.

Clinical and laboratory evaluation. Monthly up to 6 months, then every 3 months up to 24 months, then every 6 months up to month 60.

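### The 6-month response is tested unadjusted although it is built on recorded baseline values; one pre-specified baseline covariate would be a better main test, and the stated power is slightly high for the chi-square test

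*Protocol*

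**What the plan says.** **Endpoint.** Under Efficacy Parameters, a child is a responder at 6 months if three or more of the six core set variables improve by 20% or more, subject to a limit on worsening in the others. The Statistical Analysis section compares final core set values with baseline and classifies each child by this definition.

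**Test.** The same section says: "For proportional data the chi-square test, or where appropriate the Fisher's exact test, will be applied". It names no covariate for this endpoint and does not say when Fisher's test takes over.

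**Sample size.** The sample size section sizes the trial on this endpoint ("We used the PRINTO JDM definition of improvement"). For the combination arms, "the observed improvement rate was 83% after 6 months of therapy with PDN combined with MTX or CSA". For the reference arm, "We estimated that the group treated only with PDN will have a response rate equal to 53" percent. The first table row reads "PRINTO JDM def. | 53 | 30% | 0.05 | 0.8 | 34 | 40". The second row gives 46 per arm (54 with drop-out) for power 0.9; the text describes it as "for a total of 162 patients, 0.9 power, 0.05 type I error". On the comparison it says: "The trial will have 0.8 power for comparisons of the combined treatment arms (PDN+MTX or PDN+CSA) to the reference treatment arm (PDN alone").

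**The concern.** Because response is a relative change, a child's starting level may affect the chance of reaching 20% in three variables. Baseline core set values are collected in any case. If the chosen value is prognostic, an unadjusted test gives up power that could be had without recruiting another child, which matters in a rare disease with 34 evaluable children per arm.

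The stated power also comes from a variance formula that does not correspond to the chi-square test named for the analysis.

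**Working it through.** **Inputs.** From the sample size section: 53% versus 83% (difference 0.30), alpha 0.05, power 0.8 and 0.9, and 34 and 46 evaluable per arm. Sidedness is not stated. Two-sided is assumed, because the one-sided unpooled formula gives 27 and 38.

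**1. Reproduce the plan's figures.** Unpooled formula: n = (z_0.975 + z_power)² × [p1(1−p1) + p2(1−p2)] / d².
- Variance term: 0.53×0.47 + 0.83×0.17 = 0.2491 + 0.1411 = 0.3902.
- Power 0.8: (1.960 + 0.842)² × 0.3902 / 0.09 = 34.03, which the table gives as 34.
- Power 0.9: (1.960 + 1.282)² × 0.3902 / 0.09 = 45.56, which rounds up to 46.
- Drop-out: 34/0.85 = 40 and 46/0.85 = 54.1, given as 40 and 54.

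**2. The formula that fits a chi-square test.** This test pools the variance under the null: n = [z_0.975 √(2p̄(1−p̄)) + z_power √0.3902]² / d², with p̄ = 0.68 and 2p̄(1−p̄) = 0.4352.
- Power 0.8: (1.960×0.6597 + 0.842×0.6247)² / 0.09 = 36.75, so 37.
- Power 0.9: (1.960×0.6597 + 1.282×0.6247)² / 0.09 = 48.70, so 49.

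**3. Power of the named tests, pairwise, two-sided 0.05.** The exact figures come from enumerating both binomials.

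| Evaluable per arm | Stated | Chi-square, pooled approximation | Chi-square, exact | Fisher, exact |
|---|---|---|---|---|
| 34 | 0.8 | 0.767 | 0.787 | 0.693 |
| 46 | 0.9 | 0.882 | 0.887 | 0.840 |

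The smallest expected cell count at 34 per arm is 34 × (1 − 0.68) = 10.9.

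**4. Adjusting for one baseline value.** Simulation at 34 per arm: one standard-normal baseline covariate, marginal rates held at 53% and 83%, likelihood-ratio test of treatment in a logistic model, 6,000 runs per setting (Monte Carlo standard error √(0.8×0.2/6000) ≈ 0.005). The covariate strengths are assumptions.

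| Covariate log-odds per SD (assumed) | Chi-square | Adjusted logistic |
|---|---|---|
| 0 | 0.797 | 0.793 |
| 0.5 | 0.787 | 0.799 |
| 1.0 | 0.789 | 0.848 |
| 1.5 | 0.787 | 0.893 |

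A separate simulation gave 0.795 (adjusted) against 0.796 for a useless covariate and about 0.82-0.84 at 0.7-1.0 log-odds per SD. Type I error was 0.053-0.061 adjusted and 0.056-0.061 for the chi-square test.

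**5. A second covariate.** With two covariates, simulated type I error was 0.054-0.066. If neither is prognostic, size-corrected power was 0.75-0.76 against 0.78 for the unadjusted chi-square. Expected non-responders per pairwise comparison are 34 × (0.47 + 0.17) ≈ 22, which also argues for a small model.

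**The case against.** An unadjusted chi-square test is valid in a randomised trial, and adjustment is often left to the analysis plan, which is not at hand. The first part stands: nothing here is invalid or biased. The second does not dispose of the point. The Protocol is not silent; it names the test for proportions, and a better one can be named in its place.

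The shortfall against stated power is small. This stands too. Exact chi-square power is 0.013 below the stated figure in both rows and reaches 0.80 at about 36 per arm. It also depends on the comparison: with all 40 per arm analysed at the planned rates it is 0.835, and pooling the combination arms (68 versus 34) gives 0.897.

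A reader might go further in three ways that the documents do not support.
- That adjustment would recover the lost power. The Protocol gives no association between any baseline value and response, so the gain ranges from none to about 10 points over the strengths tried.
- That planned power is 0.69. That is the power of Fisher's test, a fallback that expected counts of about 11 would not normally trigger.
- That prior prednisone is a second recorded covariate. The inclusion criteria permit "prednisone >1 mg/kg/day for no more than 1 month from diagnosis", but this is an eligibility limit, and no section says that prior exposure is recorded for analysis.

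**Conclusion.** The point holds as an improvement in efficiency, with a minor correction to the power statement. The Protocol fixes an unadjusted test for an endpoint built on baseline values that it collects. Adjusting for one of them costs essentially nothing in power if it is not prognostic, adds about 1 point at 0.5 log-odds per SD and about 6 at 1.0, and has type I error similar to the chi-square test. This rests on a 53% versus 83% pairwise comparison, 34 evaluable per arm, two-sided 0.05, and assumed covariate strengths.

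The chi-square shortfall (0.79 and 0.89 exact; 0.77 and 0.88 by the pooled approximation) does not show that the trial is materially underpowered. Other features of the plan matter more for power and need separate treatment. At the 0.01 level set for multiple testing, chi-square power at 34 per arm is 0.55. If all of the 15% drop-outs count as non-responders among 40 per arm (0.53×0.85 = 45% versus 0.83×0.85 = 71%), it is about 0.66.

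**What to change.** **Statistical Analysis section.**
- Make the main test of 6-month response, for each combination versus PDN, a logistic regression adjusted for one pre-specified baseline core set value, for example the baseline physician global assessment.
- Report the standardised risk difference with its 95% CI.
- Keep the uncorrected Pearson chi-square as the sensitivity analysis.
- Add prior prednisone only if it is recorded, accepting that a second covariate may cost a little if it is not prognostic.

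**Sample size section.** State that 34 and 46 come from the unpooled-variance formula. Add that the pairwise chi-square test at two-sided 0.05 with 34 or 46 evaluable per arm has exact power of about 0.79 or 0.89 (pooled approximation 0.77 or 0.88). Say that these figures hold for that setting only.

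**Cost.** Wording and a little more analysis, with no more patients. The stated power becomes slightly less favourable, and the type I error of about 0.05-0.06 should be disclosed.

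### Core set scores are an outcome of change over time but are tested at two points only; a repeated-measures model would use the visits already collected and guard better against drop-out

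*Protocol*

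**What the plan says.** All references are to the protocol.

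- **Secondary Outcome Measures** lists "Change over time in the individual components of the JDM core set of variables".
- **Clinical and laboratory evaluation** sets the visits: "Monthly up to 6 months, then every 3 months up to 24 months, then every 6 months up to month 60".
- **Statistical Analysis** reduces the core set variables to two points: "The values at the final visit for the core set variables will be compared to the baseline values". The effect size is also built from baseline and final visit. The tests are "For continuous variables the t-test procedure or the ANOVA, will be applied as appropriate", and for other score types "Non parametric ANOVA will be applied in case of ordinal data or not-normally distributed variables; the Dunnett test will be used as a posterior test". The section does not say whether the final visit is month 6, 24 or 60, or the last visit attended.
- The same section states the principle: "Emphasis will be placed on the intention-to-treat approach rather than on analysis of only the completers of the trial".
- **Dropout Criteria** names two reasons (non-compliance, joining another trial) for which children count as treatment failures, "and dropped from the trial but included in efficacy analysis".
- **Sample size calculation** plans for 15% drop-out, as one common rate.

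**The concern.** The named method does not fit the outcome it serves. From baseline to month 24 there are 12 scheduled visits (months 1 to 6, then 9, 12, 15, 18, 21 and 24). A two-point test uses one of them, so it says nothing about the course in between.

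The second difficulty is children who leave. Counting a child as a treatment failure settles a yes/no response, but it supplies no value for muscle strength, a visual analogue scale or a functional score. The section on adverse events also lets the physician drop a child for a reason outside the two listed ones. In a two-point test such a child is either left out or represented by a value taken at another time. Either route can shift the contrast between arms, and when drop-out is unequal the two routes can shift it in opposite directions. At stake are the comparisons of each combination with prednisone (PDN) alone on the core set variables.

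**Working it through.** **The plan's own figures.** With 53% v 83%, two-sided alpha 0.05 and unpooled variance, n = (1.96 + 0.8416)² × (0.53×0.47 + 0.83×0.17) / 0.30² = 34.03 per arm, and 34/0.85 = 40. At 0.9 power the formula gives 45.56, so 46, and 46/0.85 = 54.1. Both rows of the table reproduce. They size the 6-month responder endpoint; the protocol gives no SD or effect for any core set score. At 15% drop-out, 0.15 × 40 = 6 children per arm would lack a scheduled endpoint value.

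**Assumptions for the bias check** (none is in the protocol):
- The score has SD 1 at each visit, correlation 0.6 between any two visits, and higher is better.
- The combination's benefit is 0.25 at month 3 and 0.50 at month 6.
- In each arm the fraction q with the worst change to month 3 leaves after that visit.
- The splits of drop-out between arms are illustrative.

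**Completers test.**
- The change to month 3 has variance 2(1 − 0.6) = 0.8, SD 0.894. Its covariance with the change to month 6 is 1 − 0.6 = 0.4. One SD of early change therefore carries 0.4/0.894 = 0.447 of later change.
- Removing the worst fraction q raises the stayers' mean early change by λ(q) = φ(z_q)/(1 − q) SDs: 0.109, 0.195, 0.274, 0.350 and 0.424 for q = 5, 10, 15, 20 and 25%.
- Estimated difference = 0.50 + 0.447 × [λ(q, combination) − λ(q, PDN)].

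**Last-value test.**
- Estimated difference = 0.50 − 0.25 × q(combination) + g × [q(PDN) − q(combination)] + 0.447 × [φ(PDN) − φ(combination)]. Here g is the improvement common to both arms between months 3 and 6, taken as 0 to 0.5 SD, and φ is the normal density at z_q (0.103, 0.175, 0.280 and 0.318 for 5, 10, 20 and 25%).
- At an equal 15% this is 0.50 − 0.15 × 0.25 = 0.4625. That shortfall does not need drop-out to depend on outcome; it arises because the benefit is still growing after month 3.

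| Drop-out, PDN / combination | Completers | Last value | All earlier visits used |
|---|---|---|---|
| 15% / 15% | 0.50 | 0.46 | 0.50 |
| 20% / 10% | 0.50 + 0.447×(0.195 − 0.350) = 0.43 | 0.52 to 0.57 | 0.50 |
| 25% / 5% | 0.50 + 0.447×(0.109 − 0.424) = 0.36 | 0.58 to 0.68 | 0.50 |
| 10% / 20% | 0.50 + 0.447×(0.350 − 0.195) = 0.57 | 0.35 to 0.40 | 0.50 |

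The last column is a simulation result and holds under missing at random.

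**Check with a different model.** With a random intercept and slope, a true difference of 0.60 and leaving related to early change, completers give 0.48 (20/10) and 0.36 (25/5). The last value gives 0.56 (15/15), 0.64 (20/10) and 0.71 (25/5). The analysis using earlier visits gives 0.60 throughout.

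**Drop-out that depends on the unobserved month-6 change** (0.50 SD set-up). Completers give 0.50 + 0.894 × (0.195 − 0.350) = 0.36 at 20/10 and 0.50 + 0.894 × (0.109 − 0.424) = 0.22 at 25/5. Using earlier visits gives 0.38 and 0.27, so it recovers only a little.

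**Precision.** With baseline adjustment in both methods and 15% drop-out spread over months 1 to 6, the repeated-measures model reduces the variance of the month-6 contrast by about 2 to 5%.

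**The case against.** The strongest reply is that nothing stated is wrong. The protocol never restricts the t-test or ANOVA to completers, and it keeps the listed dropouts in the efficacy analysis. How a missing score is handled is commonly left to the statistical analysis plan, which is not shown, so the absence of a rule is no finding. The protocol assumes one common drop-out rate; it does not forecast a difference between arms, and counting drop-out for inefficacy as an outcome is not such a forecast. All this stands. A reader might infer that the plan contradicts its intention-to-treat principle, or that it cannot use children who leave. The text supports neither: the final visit may be the last one attended, and the principle is left unfinished for these scores rather than contradicted.

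It is also fair that the bias depends on the mechanism. Completers are unbiased at equal drop-out in this set-up. In a variant where leaving follows the month-3 level rather than the change, with an autoregressive correlation of 0.6, completers recovered the true 0.60 even at 25% v 5%, while the last value gave 0.80. The proposed model is unbiased in the main table because drop-out there depends only on observed values.

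Finally, a reader might expect a large gain in precision. Setting a months 1 to 6 average against a single month-6 contrast shows a 2.3 to 2.7-fold smaller variance, but these are different quantities. Like for like, the ratio is about 1.02 to 1.05 at month 6 and 1.10 to 1.11 for the average.

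What the reply does not remove is the mismatch between a stated two-point method and an outcome stated as a time course.

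**Conclusion.** The point holds as a cheap improvement to a secondary analysis. The protocol fixes a two-point comparison for an outcome described over time, and it passes over visits that are already scheduled.

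The bias is possible, not demonstrated. Under the assumed unequal, outcome-related drop-out, a true 0.50 SD becomes 0.43 or 0.36 in completers, and 0.52 to 0.57 or 0.58 to 0.68 with the last value. At an equal 15% completers are unbiased and the last value gives 0.46. The direction depends on which arm loses more children and on how those children are handled.

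It would go too far to say that the results are distorted or that the core set changes are not analysed at all: a baseline-to-final comparison and an effect size are specified. The reach is limited too. The 6-month primary is a responder classification, remission and flare use survival methods with censoring, and the sample sizes reproduce.

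**What to change.** For the core set variables, replace the t-test or ANOVA by a likelihood-based repeated-measures model with arm, visit, arm-by-visit interaction and baseline value, using all scheduled visits to month 24 of all randomised children. Report each combination against PDN at month 6 and at month 24, so that the time points are named and the undefined final visit falls away. Add two sensitivity analyses: the rank-based test for clearly non-normal scores, and one for drop-out that depends on unobserved values.

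The cost is wording in the analysis section and some programming; no extra children or visits are needed. The small downside is that the model relies on missing at random and on approximate normality, which is why both sensitivity analyses belong with it.
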